## Objectives

The **main objective** of this research is to quantify and characterize the PV found in MGPT of GC patients in Alto Alentejo (Portugal).

The **specific objectives** are:

- Determine the global rate of PVs in GC patients of Alto Alentejo;
- Determine which PVs are most common in our GC population;
- Correlate the PVs found with clinical factors: Age at diagnosis; Sex; Weight; Height; Presence of other diseases (Diabetes; Arterial Hypertension; Dyslipidaemia; Stroke; Heart attack); Date of diagnosis; Stage at diagnosis; Histologic subtype; Surgery for GC; Personal history of other cancers; Familial history of GC and other cancers;
- Correlate the PVs found with prognostic factors: 12-month survival rate; mortality.

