### Setting

This study takes place at the Unidade Local de Saúde do Alto Alentejo (ULSAALE). The MGPT was always performed in the same laboratory (Germano de Sousa – Centro de Genética Laboratorial) using peripheral blood samples from patients with GC.

Two types of MGPT were used:

- MGPT 4005 (15 genes): APC, ATM, BLM, BMPR1A, CDH1, CTNNA1, EPCAM, MLH1, MSH2, MSH6, PMS2, PTEN, SMAD4, STK11/TP53.
- MGPT 4013 (30 genes): ATM, BARD1, BLM, BRCA1, BRCA2, BRIP1, CDH1, CHEK2, EPCAM, FANCC, MLH1, MRE11A, MSH2, MSH6, MUTYH,

NBN, NF1, PALB2, PMS2, PTEN, RAD50, RAD51C, RAD51D, RECQL4, RINT1, SLX4, SMARCA4, STK11, TP53, XRCC2.

The majority of patients with GC were tested with MGPT 4005. Patients with neoplasms other than GC or with a family history of other neoplasms were tested with MGPT 4013. The decision to perform MGPT and the choice of panel type were made in multidisciplinary consultation.

The recruitment process takes place between January 2023 and December 2024. All data will be collected and entered in a database until September 2025

The manuscript for publication will be written between October and November 2025.

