### **Participants**

Eligibility criteria:

- Adult patients (over 18 years old) with a histologically proven diagnosis of gastric adenocarcinoma that have done MGPT between 2023 and 2024;
- Ability to understand and speak Portuguese and/or English language;
- Ability to reliably provide informed consent for inclusion in the study.

There are no matched or randomized groups.

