#### **Data sources**

The variables related to the patient's clinical history and personal data will be collected through a questionnaire administered during a personal interview and supplemented by consultation of each patient's digital medical record in order to obtain more detailed information on the variables characterising the disease and the results of the MGPT.

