#### **Study size**

The sample calculation takes into account the number of annual cases of GC recorded in Alto Alentejo (65 cases in 2020, data from National Oncologic Registry). Therefore, the sample calculation suggests that it should include 56 patients with GC, with a confidence level of 95% and a margin of error of 5%.

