**Table 2 - Variables / Measurements**

Type of Variable	Name of Variable	Measurements
MGPT Outcomes variables	MGPT	positive (1) or negative (0)
	PV	integer number
	Likely pathogenic variables (LP)	integer number
	Name of genes with PV	descriptive
	PV in each gene	integer number
	VUS	integer number
Potential confounders variables	Age at diagnosis	Years
	Sex	Female(1)/Male(0)
	Weight	Kg
	Height	cm
	Body mass index	Kg/m 

	Presence of other diseases: Diabetes; Arterial Hypertension; Dyslipidaemia; Stroke; Heart attack);	Yes(1)/No(0) for each disease
	Stage at diagnosis (AJCC staging system);	0, I, IIa, IIb, III, IVa, IVb
	Histologic subtype;	Intestinal (1); Diffuse (2); Mixed (3)
"Exposures" variables	Personal history of other cancers	Yes (1)/No (0)
	Types of other cancer in GC patient	descriptive
	Familial history of GC	Yes (1)/No (0)
	Age of onset of each familial case of GC	integer number
	Familial history of other cancers (specifying)	descriptive
	Age of onset of each familial case of other cancers	Years
Prognostic related variables	12-months survival	Yes (1)/No(0)
	Death due to GC	Yes (1)/No(0)
	Date of death	mm/yyyy
Other variables:	Date of diagnosis	mm/yyyy
	Localization of tumor	Cardia / Fundos / Body / Antrum/pyloro
	Time since diagnosis until the current moment	months
	Surgery for GC	Yes (1)/No (0);
	Type of surgery	Total gastrectomy (1); Subtotal gastrectomy (0)
	Date of Surgery	mm/yyyy
	Histologic staging after surgery	0, I, IIa, IIb, III, IVa, IVb
	Underwent chemotherapy	Yes (1) / No (0)
	Type of chemotherapy	descriptive

	Cycles of chemotherapy	integer number
	Positive MGPT is considered when it is found at least one PV in one gene of teste	A comparative analysis will be made between the individual characteristics and tumor characteristics of positive MGPT cases with those with negative MGPT.

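### Entry is dated by the gene-panel test with no limit on the date of diagnosis, so new cases may be pooled with earlier-diagnosed survivors and the plan has no prespecified way to show whether this matters

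*Combined protocol and SAP*

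**What the plan says.** Under Participants, the clinical entry criterion is a "histologically proven diagnosis of gastric adenocarcinoma that have done MGPT between 2023 and 2024", together with adult age, language and capacity to consent. No section limits the date of diagnosis or the time from diagnosis to test.

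Setting gives a recruitment period ("The recruitment process takes place between January 2023 and December 2024") and describes the route to testing: "The decision to perform MGPT and the choice of panel type were made in multidisciplinary consultation". Under Data sources, history and personal data are "collected through a questionnaire administered during a personal interview", supplemented by the medical record.

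The first specific objective is to "Determine the global rate of PVs in GC patients of Alto Alentejo". The factors to be correlated with PV status include "Date of diagnosis; Stage at diagnosis; Histologic subtype". The Bias section states that the criteria give a representative sample without selection bias, and promises an analysis that takes timing into account, with no method. Study size works from "the number of annual cases of GC recorded in Alto Alentejo (65 cases in 2020, data from National Oncologic Registry").

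Table 2 lists the date of diagnosis (month and year) and "Time since diagnosis until the current moment" in months. It does not list the date of the panel test.

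**The concern.** A cohort entered by test date can hold two kinds of patient: those tested soon after diagnosis, and those diagnosed before 2023 who were still alive and were tested later. The second kind has passed a survival filter and probably a referral filter. If either filter acts differently on carriers and non-carriers, the pooled PV rate departs from the rate among new cases.

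Three parts of the plan depend on this. The Risks and Benefits section intends to compare the result with a literature prevalence of 3-5% and links it to a possible case for population screening. The Bias section claims representativeness. The Objectives call for PV status to be correlated with date of diagnosis. That last comparison is the most exposed: germline status is fixed, so a difference between diagnosis periods in this cohort may reflect who lived to be tested and who was referred.

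**Working it through.** **1. The plan's own figure.** Inputs: N = 65, 95% confidence, margin 5 points (Study size). The expected proportion is not stated; I assume the conventional 0.5.

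- n0 = 1.96² × 0.5 × 0.5 / 0.05² = 384.15
- n = n0 / (1 + (n0 − 1)/N) = 384.15 / (1 + 383.15/65) = 55.7, rounded up to 56

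The stated 56 reproduces, but only for a closed population of one year's recorded cases.

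**2. Population sampled against population counted.** Recruitment runs for 24 months and the date of diagnosis is open. Even if only diagnoses in 2023-2024 counted, and 65 a year held (assumption), N would be 130 and the same formula gives 97.3, that is 98. With no diagnosis window, N is not fixed. The calculation and the eligibility rule therefore refer to different populations.

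**3. What moves the PV rate.** Let p be the rate among new cases and R the chance that a carrier reaches testing relative to a non-carrier, acting only on earlier-diagnosed patients. Their rate is pR/(pR + 1 − p). With a share s diagnosed earlier, the pooled rate is (1 − s)p + s × pR/(pR + 1 − p). The documents give neither R nor s; p = 5% is taken from the upper end of the literature range they quote.

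| R | Rate, earlier-diagnosed | Pooled, s = 25% | Pooled, s = 40% | Pooled, s = 50% |
|---|---|---|---|---|
| 0.5 | 2.6% | 4.4% | 4.0% | 3.8% |
| 1 | 5.0% | 5.0% | 5.0% | 5.0% |
| 2 | 9.5% | 6.1% | 6.8% | 7.3% |

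At R = 1 nothing moves, whatever the mix.

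**4. PV status by diagnosis period.** The odds of a PV are p/(1 − p) in new cases and Rp/(1 − p) in earlier-diagnosed cases, so the odds ratio between periods equals R. With R = 2 the data would show 9.5% against 5.0% although the underlying rate had not changed. Pooling does not dilute this contrast.

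**5. PV status by stage or histology.** Suppose 40% of new cases are stage IV, and 20% of these survive to testing against 70% of the others (all assumed). Stage IV is then 0.4 × 0.2 / (0.4 × 0.2 + 0.6 × 0.7) = 0.08/0.50 = 16% of the earlier-diagnosed. That is a changed stage mix. If the chance of testing depends on stage but not on PV status within stage, carriers and non-carriers in each stage are thinned by the same factor and the PV-by-stage odds ratio is unchanged. It is distorted only if selection depends jointly on both.

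**6. Scale against sampling error.** Three carriers in 56 (5.4%) has an exact 95% interval of 1.1% to 14.9%, wider than any shift in the table. That interval does not, however, allow for selection.

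**7. What the listed variables allow.** Date of diagnosis separates pre-2023 from 2023-2024 diagnoses. Without a test date, the diagnosis-to-test interval cannot be derived, and the time-since-diagnosis variable runs to an end point that is not a fixed date.

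**The case against.** The case on the other side is substantial, and much of it stands.

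- A reader might infer that the results describe no defined population. They do not show that: the cohort is adults with gastric adenocarcinoma tested in 2023-2024 who can consent. What is missing is the link to the stated target.
- A reader might infer that survivors and new cases cannot be told apart. They can, because the date of diagnosis is recorded. The plan simply does not say the split will be made.
- A reader might infer that the PV rate and the stage and histology comparisons are biased. The documents give no evidence that carriers differ in survival to testing or in referral, and a shifted stage mix is not a biased association.
- The target is worded as patients with gastric cancer, not new cases. The one-year count is a sample-size input, so it shows a mismatch and does not by itself define the target.
- Statistical methods (d) mentions varying the inclusion criteria, and Setting ends data collection in September 2025, which bounds the open-ended time variable. Both help, but the first names no specific analysis and the second is not a per-patient cut-off.
- Making 2023-2024 diagnoses the primary population would be costly. If 40% were diagnosed earlier, 56 becomes 0.6 × 56 ≈ 34, and 2 carriers in 34 has an exact 95% interval of 0.7% to 19.7%. It would also leave in place selection through referral, consent and interview, and a patient diagnosed in January 2023 and tested in December 2024 is still a survivor of nearly two years.

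The last point is decisive against changing the primary population. None of the points supplies the missing test date or a prespecified split.

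**Conclusion.** The point holds as a gap in design and reporting. Eligibility permits a mix of new and earlier-diagnosed patients, nothing elsewhere closes it, and it fits neither the one-year case count nor the representativeness statement. The documents do not show that the mix occurred or how large it is. Any bias in the PV rate requires carriers to differ in survival to testing or in referral. Under the wholly assumed inputs above, a 5% rate would be seen as 3.8% to 7.3%, on either side of the upper benchmark but well inside sampling error. The comparison by date of diagnosis is the most exposed, because there the selection ratio passes straight into the odds ratio. The change is cheap and worth making before results are examined.

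**What to change.** 1. Add the panel sample date to Table 2 and report the distribution of the diagnosis-to-test interval.
2. Keep all eligible patients in the main estimate. Prespecify the PV rate and the clinical-factor comparisons separately for patients diagnosed in 2023-2024 and before 2023.
3. Under Statistical methods (d), name restriction to 2023-2024 diagnoses, or to a short stated diagnosis-to-test interval, as a sensitivity analysis.
4. Replace the open-ended time-since-diagnosis variable with time to a fixed data cut-off.
5. State in the conclusions that the rate describes tested, consenting patients and not all new gastric cancer cases in Alto Alentejo, and amend the representativeness statement to match.

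The cost is one extra date per patient from the laboratory report and some wording; nobody is dropped. The split rows will have wide intervals and should be read as descriptive. Selection through referral, consent and interview remains and should be acknowledged.

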### **Variables / Measurement**

### Table 2

#### **Data sources**

The variables related to the patient's clinical history and personal data will be collected through a questionnaire administered during a personal interview and supplemented by consultation of each patient's digital medical record in order to obtain more detailed information on the variables characterising the disease and the results of the MGPT.

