#### **Bias**

Efforts to address potential sources of bias:

**Clear Inclusion and Exclusion Criteria:** The inclusion criteria are clear to select patients that are representative of the target population (patients with gastric adenocarcinoma) and that there is no bias in participant selection.

**Control of Confounding Factors:** There are some confounding factors that may influence the study results, such as age, sex, Weight; Height; Body mass index; **Presence of other diseases:** Diabetes; Arterial Hypertension; Dyslipidaemia; Stroke; Heart attack). This will be achieved through appropriate statistical techniques or data stratification during analysis.

**Uniformity in data records:** There was uniformity in the data recorded for each participant who agreed to be submitted to MGPT, minimizing the variability between records or the missing clinical data.

**Consistent and Accurate Data Collection:** This will be achieved through adequate training of interviewers or data collection personnel and the use of standardized data collection protocols.

**Blind Data Assessment:** After collection, the data will be pseudo-anonymized so that the researcher who analyses the data will not have access to the patient's identifying data.

**Time-Sensitive Analysis:** Data analysis takes into account the timing of data collection relative to relevant clinical events.

**Sensitivity Analysis:** It will be performed a sensitivity analyses to assess the robustness of the results across different results of MGPT and clinical factors.

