### **Risks and Benefits**

The main benefits and expected outcomes of the study are the contribution to a better understanding of GC carcinogenesis, which could improve the diagnostic and therapeutic approach of GC patients and their relatives. In addition, this research may help to clarify whether the prevalence of hereditary GC is higher than that described in the literature (3-5%) (4,5), and may justify screening the population for this disease.

However, the use of MGPT is not without important risks, namely the identification of variants of undetermined significance (VUS), which requires careful integration of all clinical and genetic information for correct personal and family counselling. Whenever necessary, VUS carriers (as well as patients with identified PVs) will be referred to the Portuguese Institute of Oncology in Lisbon (IPOLFG) for family risk and genetic counselling. Other potential risks of this study include the psychological stress and anxiety caused by the survey and MGPT results, the need to travel to participate in the study, and the fact that the study is being conducted by non-geneticist researchers, which limits the immediate counselling that can be provided. In this way, we will have the collaboration of the psychologists of the Day Hospital, and our close collaboration with the Germano de Sousa Genetics Laboratory and the IPOLFG teams will allow an adequate response to technical questions about the MGPT. Finally, it should be noted that this observational study will only analyse the MGPT results of CG patients and will not propose any additional intervention for patients or their families.

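### Family history is taken by interview from patients already tested, with no masking to the MGPT result, so the PV–family history association could be inflated

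*Combined protocol and SAP*

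**What the plan says.** Under Data sources, clinical history and personal data are to come from a "questionnaire administered during a personal interview", with the patient's electronic record as a supplement. The stated purpose of the record is to give "more detailed information on the variables characterising the disease and the results of the MGPT"; family history is not named there.

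Under Participants, eligible patients are those "that have done MGPT between 2023 and 2024". Under Setting, data collection and entry run to September 2025, about nine months after the last possible test.

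Table 2 lists family history of gastric cancer and of other cancers, with relatives' ages of onset, among the "exposures" variables. The Objectives include correlating PVs with these histories, and the analysis compares MGPT-positive with MGPT-negative patients.

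The Blind Data Assessment item under Bias applies after collection and provides that "the researcher who analyses the data will not have access to the patient's identifying data". The same section promises interviewer training, standardised collection and an analysis sensitive to timing. It does not name recall or interviewer bias.

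Setting also shows that some history was known before testing: "Patients with neoplasms other than GC or with a family history of other neoplasms were tested with MGPT 4013".

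**The concern.** The exposure (family history) is recorded by asking people, and the grouping variable (MGPT result) may already be known to the person answering, the person asking, or both. Someone told that they carry a PV has a reason to search the family's history, and an interviewer who knows the result has a reason to probe. A non-carrier and that patient's interviewer have less. If capture of true history is better in carriers, an association appears even where none exists, or a real one is exaggerated.

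At stake is one of the plan's specific objectives. The overall PV rate and the list of genes involved are not affected.

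**Working it through.** **1. The plan's own figure.** The only design figure is 56 patients (Study size). With z = 1.96, margin 0.05 and an assumed proportion of 0.5 (not stated in the plan): n0 = 1.96² × 0.25 / 0.05² = 384.1. With the finite population correction for 65 cases, n = 384.1 / (1 + 383.1/65) = 55.7, rounded up to 56. It reproduces, and supplies the sample size used in step 4.

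**2. What is and is not masked.** Testing precedes inclusion (Participants), and the interview questionnaire is written in the future tense (Data sources). The local ethics approval carries a 2024 reference (Ethical Issues), while testing began in 2023. It is therefore plausible that many interviews follow the result, but no passage fixes the order. The only blinding is of identity, for the analyst, after collection, when any difference in reporting is already in the data.

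**3. Possible size of the bias.** The documents give no capture rates and no family-history prevalence in the two groups, so all inputs here are assumptions. Let the true prevalence be f in both groups (true odds ratio 1), with capture s1 in positives and s0 in negatives and no false reports:

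OR = [f·s1 / (1 − f·s1)] / [f·s0 / (1 − f·s0)]

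For f = 0.20, s1 = 0.95, s0 = 0.70: (0.19/0.81) / (0.14/0.86) = 0.2346 / 0.1628 = 1.44.

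| Capture, positives / negatives | f = 10% | f = 20% | f = 30% |
|---|---|---|---|
| equal | 1.00 | 1.00 | 1.00 |
| 95% / 90% | 1.06 | 1.07 | 1.08 |
| 95% / 80% | 1.21 | 1.23 | 1.26 |
| 95% / 70% | 1.39 | 1.44 | 1.50 |
| 90% / 60% | 1.55 | 1.61 | 1.68 |
| 95% / 60% | 1.64 | 1.72 | 1.82 |

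The direction is not guaranteed. With a true odds ratio of 3 and 20% prevalence in negatives, prevalence in positives is 0.75/1.75 = 0.4286. Equal 80% capture then gives (0.3429/0.6571) / (0.16/0.84) = 2.74, which is bias toward the null. Capture of 100% versus 80% gives (0.4286/0.5714) / (0.16/0.84) = 3.94.

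**4. Sensitivity to one patient.** At the 3–5% cited under Risks and Benefits, 56 × 0.03 = 1.7 and 56 × 0.05 = 2.8, so about 2 to 3 carriers. Take 3 carriers and 53 negatives, 11 of whom report a history (about 20%, assumed). The number of ways to choose 3 from 56 is 27,720.

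- 2 of 3 carriers with history (13 in all): Fisher p = (78 × 43 + 286) / 27,720 = 3,640 / 27,720 = 0.13.
- 3 of 3 carriers with history (14 in all): Fisher p = 364 / 27,720 = 0.013.

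In both cases the less extreme tables are all more probable than the observed one, so the two-sided value equals the upper tail. One history recorded differently crosses the conventional threshold.

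**The case against.** Several points on the other side are sound.

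- **Order of events.** A reader might infer that the documents establish that patients knew their result at interview. They do not. Having been tested is not the same as having been told, recruitment spans the testing period, and September 2025 is an end date, not an interview date. The remark that records were uniform for everyone who agreed to testing could even describe recording around the time of the test. This stands, so the point is conditional.
- **Referral.** A reader might also infer that medical records differ by result because "VUS carriers (as well as patients with identified PVs) will be referred" for family-risk counselling. This is not supported. Referral is only as necessary, patients with only a VUS count as MGPT-negative, referral is to another institution with no stated return of pedigrees, and the record is not named as a source of family history.
- **Existing safeguards.** Training and standardised collection help with consistency, but they do not conceal the result. The timing item sets no rule for interview versus disclosure. This part of the objection does not remove the gap.
- **Size.** The capture rates are invented, and small or no bias is compatible with the plan. With about three carriers, random error is very large: for 1 of 3, the exact 95% interval is about 1% to 91%. This stands. The one-patient example shows fragility as much as recall bias.
- **Scope.** Personal cancer history is less exposed, because the patient's own record can verify it. This also stands.

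**Conclusion.** The concern holds in a conditional form. The plan takes family history by interview from patients already tested, leaves the order of interview and disclosure unstated, and masks neither party to the result. Where disclosure comes first, the PV–family history association could be inflated. It would go too far to say that it will be: equal under-reporting would pull a real association toward the null.

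The size cannot be derived from the documents. Under the assumptions in the table, spurious odds ratios run from 1.00 with equal capture to 1.82 at the widest gap tried. The few expected carriers make the comparison sensitive to a single record.

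The point concerns family history and a specific objective, not the PV rate. Choosing the panel by history could also link history to PV detection; that is a separate mechanism and is not counted here. The change is worth making before the data are locked, because undated entries are hard to separate afterwards.

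**What to change.** - **Data sources and Table 2:** for each family-history item, record its source and whether it was documented before or after the MGPT result was disclosed. State when the interview takes place relative to disclosure.
- **Variable analysed:** use history documented at the pre-test multidisciplinary consultation where it exists, and flag any item first reported after the result.
- **Statistical methods, item d:** pre-specify a sensitivity analysis of the PV–family history association restricted to pre-result history.
- **Interviews not yet held:** where feasible, hold them before disclosure or have existing staff who do not know the result conduct them. This concerns the interview only, not when results are given.
- **Bias:** name recall and interviewer bias, and state that the present blinding covers identity only.

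The cost is protocol wording, one dated source field per family-history item and some chart review. The drawback is that pre-test history may be thinner. Setting shows that other neoplasms and family history of other neoplasms were known when the panel was chosen, but not that familial gastric cancer or relatives' ages of onset were recorded. For that reason the restricted analysis is a sensitivity analysis, and interview data should be kept and flagged, not discarded.
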